12.5 Site Closure Visit27

13. RISK/BENEFIT ANALYSIS27

13.1 Expected Risks:27

13.2 Expected Benefits:27

13.3 Conclusion:28

14. DATA ANALYSIS28

14.1 Analysis Sets28

I N M O D E

Safety and Efficacy of Trim II for Non-invasive Lipolysis and Circumference Reduction of Abdomen.

Protocol No: DO609924A SIRB ID: 8659

Rev. Date: Jun 3 2022

14.2	Statistical Analysis.....	28
15.	DATA MANAGEMENT PLAN	28
16.	REFERENCES	28
17.	INVESTIGATOR STUDY ACKNOWLEDGMENT	29
	APPENDIX 1.0: TIME AND EVENTS SCHEDULE.....	30
	APPENDIX 2.0. MEASURING FAT THICKNESS AT THE TREATED AREA USING ULTRASOUND IMAGING (USI) DEVICE.....	31
	APPENDIX 3.0: PHOTOGRAPHY	32
	APPENDIX 4.0: CIRCUMFERENCE MEASUREMENTS	33
	APPENDIX 5.0: SCALES.....	35

2. Introduction & Study Rationale

Unwanted excess fat is a common medical and aesthetic concern. Surgical interventions may yield definitive results of fat reduction and body contouring, however invasive modalities require long recovery time and may be associated with significant risks.

A variety of non-invasive body treatments are available for medical aesthetic indications such as circumference reduction and fat lipolysis. These include devices based on optical energy such as lasers and Intense Pulsed Light (IPL), devices based on ultrasound technologies, radiofrequency (RF), Cryolipolysis, suction- massage, or combined technologies.

Non-invasive modification of the adipocyte by the various energies involves one of several mechanisms such as thermal augmentation of normal fat metabolic pathways, thermal destruction, cavitation destruction, or creation of a temporary adipocyte cell membrane pore¹. As a non-invasive option, these technologies have been developed to reduce cellulite and body circumference with minimal recovery time and risks².

Through these mechanisms, the final result is that the sizes of the adipocytes are either temporarily or permanently reduced and/or the number of adipocytes is reduced, which will result in a measurable reduction of fat and circumference of the treated area.

RF technology for fat related indications is vastly used and clinically studied. RF delivers a thermal stimulus to the skin and subcutaneous adipose tissue causing neocollagenesis and thickening of the dermis and enhancement of lipolysis - fat cell metabolism, resulting in reduction of adipose tissue volume and circumferences³.

[Redacted text block]

[Redacted text block]

[Redacted text block]

3. Definitions, Acronyms and Abbreviations

- RF - Radiofrequency
- IPL – Intense Pulsed Light
- EMS - Electrical Muscle Stimulation

I N M O D E

Safety and Efficacy of Trim II for Non-invasive Lipolysis and Circumference Reduction of Abdomen.

Protocol No: DO609924A SIRB ID: 8659

Rev. Date: Jun 3 2022

NMES - Neuromuscular Electrical Stimulation

USI – Ultrasound Imaging

AE - Adverse Events

SAEs - Serious Adverse Events

UADEs - Unanticipated Adverse Device Effects

ICF – Informed Consent Form

CRF- Case Report Form

[figure not shown]
4. Device Description

The Trim II applicator is a hands-free medical aesthetic device applying combined bi-polar RF energy and muscle activation.

[figure not shown]
The non-invasive bi-polar RF treatment is targeting the dermal and subdermal tissues. The EMS repeatedly contracts muscles by passing electrical currents through electrodes contacting the treated body area.

[Redacted text]

[Redacted text]

[Redacted text]

I N M O D E

Safety and Efficacy of Trim II for Non-invasive Lipolysis and Circumference Reduction of Abdomen.

Protocol No: DO609924A SIRB ID: 8659

Rev. Date: Jun 3 2022

[REDACTED]

The System provides individual adjustment of RF and EMS intensity level to achieve maximum efficacy, safety and comfort for each patient. The System provides enhanced safety while minimizing possible side effects by constantly monitoring RF parameters.

Another safety feature is a hand-held switch (Figure 2) that interrupts the treatment process and switches the system to pause state until the operator re-enables it. The patient can use the hand-held switch to pause the treatment if the discomfort becomes excessive.

5. Study Objectives

The Primary Objective of this trial is to evaluate the safety and efficacy of the Trim II treatment for lipolysis and abdominal circumference reduction.

6. Study Endpoints

6.1 Primary Endpoints

- Efficacy of the Trim II treatment for lipolysis and abdominal circumference reduction.
Evaluation of change in abdomen circumference using tape measurements in cm at the 3 months follow-up visit comparing to baseline.
Success criteria: Statistically significant reduction in abdominal circumference tape measurements at the 3 months follow-up visit compared to baseline.
* The primary effectiveness endpoint will be calculated based on those patients whose weight remains stable during the study period. A subject is defined as having maintained her weight during the treatment period if it remained within $\pm 3\%$ (inclusive) of baseline for the respective period.

 I N M O D E	Safety and Efficacy of Trim II for Non-invasive Lipolysis and Circumference Reduction of Abdomen.	
	Protocol No: DO609924A SIRB ID: 8659	Rev. Date: Jun 3 2022

- Safety of the Trim II treatment for lipolysis and abdominal circumference reduction. The occurrence of adverse events will be followed throughout the whole study. Observation, assessment and recording of potential reactions by the investigator. Evaluations will be done immediately after each treatment and at the follow-up visits. The frequency, severity and causality of reactions will be recorded.

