6.2 Secondary Endpoints

- Efficacy of the Trim II treatment for fat and circumference reduction in abdomen, as assessed by two blinded evaluators. Evaluation of photographs at baseline and 3 months follow-up. Success criteria: Correct identification of baseline and 3-month follow-up visit photographs in at least 70% of treated subjects by two blinded evaluators.
- Change in abdominal fat thickness measured by ultrasound imaging (USI) at the 3 months follow-up visit comparing to baseline. Success criteria: statistically significant change in fat thickness measurements at the 3 months follow-up visit compared to baseline.
- Evaluation of change in histological samples at 3 months follow-up visit comparing to baseline. Success Criteria: Effect on fat tissue with no adverse effect in dermal tissue
- Subject's satisfaction with study treatment at 3 months follow-up visit. Subject's satisfaction with the therapy results evaluated through the Subject Satisfaction Questionnaire (5-point scale) as follows: +2 = Very satisfied; +1 = Satisfied; 0 = Indifferent; -1 = Disappointed; -2 = Very disappointed.
- Therapy comfort during the study treatment. Subjects will be asked to classify skin reactions (subjective evaluation) and will rate discomfort using visual analog pain scale from 0 (no pain) to 10 (intolerable pain) immediately after each treatment session.

7. Study Population

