Appendix 2.0. Measuring Fat Thickness at the Treated Area using Ultrasound Imaging (USI) Device

- At screening visit, the therapist will mark the rectangle of the treatment area according to the applicators setting with white pencil.
- Two US measurement points will be selected and images will be captured (according to the applicators positioning)
- A transparency will be created at baseline for each patient, with treated area, identification marks (umbilicus, spots/moles) and the measurements points marked, to ensure USI of the same point at baseline and FU visit.
- US probe should be applied to measure abdominal subcutaneous fat in the area of the two measurement points (identified according to the transparency).
- Each measurement of fat later thickness should be repeated 2 times and an average value will be recorded.

	Safety and Efficacy of Trim II for Non-invasive Lipolysis and Circumference Reduction of Abdomen.	
	Protocol No: DO609924A SIRB ID: 8659	Rev. Date: Jun 3 2022

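### The primary endpoint claims efficacy for lipolysis and circumference reduction, but its only success rule is a tape measurement, which cannot alone support the lipolysis half

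*Combined protocol and SAP*

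**What the plan says.** Section 5 states the objective as to "evaluate the safety and efficacy of the Trim II treatment for lipolysis and abdominal circumference reduction". Section 6.1 and the synopsis repeat the pairing as the title of the primary efficacy endpoint: "Efficacy of the Trim II treatment for lipolysis and abdominal circumference reduction". The variable under that title is "Evaluation of change in abdomen circumference using tape measurements in cm at the 3 months follow-up visit comparing to baseline", and success is "Statistically significant reduction in abdominal circumference tape measurements at the 3 months follow-up visit compared to baseline". No fat criterion and no minimum size is attached. Section 6.1 adds that the calculation uses subjects whose weight stayed within ±3% of baseline.

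Section 4 describes the device as a "hands-free medical aesthetic device applying combined bi-polar RF energy and muscle activation". The muscle stimulation is delivered to the same treated area, the abdomen.

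Fat is addressed among the secondary endpoints in 6.2: "Change in abdominal fat thickness measured by ultrasound imaging (USI) at the 3 months follow-up visit comparing to baseline". Success there is a significant *change*, with no direction given. Appendix 2.0 sets out the method: "US probe should be applied to measure abdominal subcutaneous fat in the area of the two measurement points". Histology, also secondary, looks for an effect on fat tissue in 8 subjects (8 to 10 in one synopsis entry). No visible text makes the primary conclusion depend on either measure.

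**The concern.** The label makes two claims and the rule tests one of them. Section 2 argues in one direction only: reducing fat cells will reduce fat and circumference. It does not say that a smaller circumference shows that fat was lost. A significant tape result would therefore satisfy an endpoint titled efficacy for lipolysis even if ultrasound fat thickness had not moved.

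What is at stake is the wording of the trial's main conclusion. The plan already collects the data that could support or contradict the word *lipolysis*, but it leaves them outside the decision.

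**Working it through.** **Label against rule.**

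- Circumference reduction (synopsis, 5, 6.1): measured by tape at baseline and 3 months, and tested by the primary rule.
- Lipolysis (synopsis, 5, 6.1): no component of the primary rule measures fat. The fat measures, ultrasound and histology, appear only in 6.2.

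**Are non-fat explanations excluded?**

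- Design: the synopsis describes a prospective open-label study. No control arm is described, and no arm separates RF from muscle stimulation.
- Weight: the ±3% rule limits weight change but allows some within the band.
- Posture and technique: Appendix 4.0 fixes tape height, tension, and arm and head position. It says nothing about breathing phase or relaxation of the abdominal muscles.
- Muscle: section 4 says the stimulation contracts muscle. No visible text says that this alters circumference.

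Non-fat causes are therefore limited in part but not excluded.

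**How small a tape change meets the rule?** The visible text gives 70 subjects with no power, effect size or SD, so there is no stated calculation to reproduce. The following is context only.

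- Inputs: n = 70 (7.1); paired t-test, two-sided 0.05 (14.2); SD of the tape change 2 to 4 cm (assumed).
- Smallest significant observed mean change = t(0.975, n−1)/√n, in SD units.
- At n = 70: 1.995/√70 = 0.238 SD, which is 0.48, 0.72 and 0.95 cm for SD 2, 3 and 4 cm.
- The weight-stable subset may be smaller. If 80% were stable (assumed), n = 56 and 2.004/√56 = 0.268 SD, which is 0.54, 0.80 and 1.07 cm.

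**Illustration with no fat loss.** Suppose some non-fat cause lowered the tape reading by a true mean of 1 cm. This is an assumption; the documents give no size for any such effect. From the noncentral t distribution at n = 70, the chance of meeting the primary rule is 0.985, 0.785 and 0.541 for SD 2, 3 and 4 cm. With a 0.5 cm shift it is 0.541, 0.279 and 0.177.

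**Effect of requiring both results.** If ultrasound thickness truly does not change, the chance of a significant *reduction* on a two-sided 0.05 test is 0.05/2 = 0.025. A lipolysis conclusion that needs both results can then be reached no more often than that, whatever the tape does. Because both must succeed, alpha need not be split. If each test had 90% power (assumed), joint power would be 0.9 × 0.9 = 0.81 when the tests are independent, and up to 0.90 when they are perfectly correlated. Actual ultrasound power cannot be computed, because the documents give no effect or SD for fat thickness.

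**The case against.** The best reply is that the trial as a whole does examine fat. Ultrasound thickness is a pre-specified secondary endpoint with its own significance criterion and a standardised method. Histology looks directly at fat tissue, the blinded photograph review is labelled as fat and circumference reduction, and caliper skinfolds are taken through follow-up. The objective is stated for the whole trial, and the format of the final report is left to the sponsor. All of this stands. A reader might infer that the trial will yield no evidence on fat, or that lipolysis will be reported whatever the ultrasound shows. The documents support neither: the fat data will exist, and no passage says how a discordant result would be reported. The gap is that nothing in the plan ties the two together.

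A reader might also infer that muscle stimulation will itself produce the tape reduction. The documents do not say that it reduces circumference, by how much, or that any effect lasts to 3 months after the last treatment. Parts of sections 2 and 4 are redacted and may discuss it. By their titles, references 4 to 7 concern electrical stimulation and abdominal muscle, which makes a muscle effect a plausible example but not a documented mechanism. The point does not need it, because the rule contains no fat measure at all.

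Finally, Appendix 4.0 and the weight rule are real controls, and the sensitivity of the tape test to any cause is shared by every single-arm before-and-after comparison. That is correct. The threshold figures give context; they do not measure the labelling gap.

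**Conclusion.** The point holds for the lipolysis half of the label only. The tape is an appropriate measure of circumference, and a significant reduction supports that half as a change from baseline without a control. It does not by itself support lipolysis, because fat is not in the rule and other explanations are not excluded. It would go too far to say that a lipolysis conclusion drawn from the tape would be false: it would be unsupported by the tape, and the ultrasound could still bear it out.

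No figure in the documents fixes the size of the problem. For context, the tape rule is met at an observed mean reduction of about 0.24 SD with 70 analysed, and slightly more if the weight-stable subset is smaller. The values in centimetres rest on an assumed SD of 2 to 4 cm, and the success probabilities also rest on an assumed non-fat shift. This is a wording and decision-rule correction worth making because it is cheap; it does not show that the planned test is wrong.

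**What to change.** - **Synopsis, 5 and 6.1:** limit the primary tape success statement to abdominal circumference reduction.
- **Synopsis and 6.2:** change the ultrasound success criterion from a significant change to a significant reduction in fat thickness at 3 months.
- **Synopsis, 6.2 and 14.2:** state that a lipolysis conclusion requires both a significant tape reduction and a significant ultrasound reduction, each at two-sided 0.05 with no alpha split.
- **14.2, consistent with 6.1 and 14.1:** name one analysis set for both tests. At present 6.1 restricts the primary calculation to weight-stable subjects, 14.1 defines a broader performance set, and the ultrasound test is assigned to neither.

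The change adds no visit, procedure or subject, since ultrasound is already scheduled at baseline and 3 months. The cost is that the lipolysis claim becomes harder to make: it will depend on an ultrasound test whose power is unknown. Requiring both results does not supply a control arm, so the ultrasound result would still be an uncontrolled change from baseline and should be described that way.

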7.2 Subject Withdrawal and Replacement

Subjects enrolled in the study can discontinue their participation at any time for any reason without prejudice or reduction in the quality of their medical care. The investigators or sponsor can terminate a

	Safety and Efficacy of Trim II for Non-invasive Lipolysis and Circumference Reduction of Abdomen.	
	Protocol No: DO609924A SIRB ID: 8659	Rev. Date: Jun 3 2022

subject's participation in this study to protect the subject's health or if the subject fails to follow directions resulting in noncompliance to study procedures. Subjects who withdraw or are terminated from the study may be replaced to ensure that at least 70 subjects have completed the study. Subjects who fail to complete the treatment will be replaced and will not be evaluable.

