8.5 Table 1 – Clinical Evaluation Measurements and Tools

Measurement	When to conduct	Method
Height	Baseline, Prior to every treatment and at follow-up's visits	Scale
Weight		Scale
BMI		Calculation
Circumference	Baseline, Prior to every treatment and at follow-up's visits	Tape Measurement (Appendix 4.0)
Caliper	Baseline, Prior to every treatment and at follow-up's visits	Caliper
Photographs	Baseline, and at follow-up's visits	Standardized digital photographs (Appendix 3.0)
Urine pregnancy test	Baseline, Prior to every treatment and at last follow-up visit (3 months)	Urine pregnancy test
Ultrasound imaging	Baseline and last follow-up visit	Abdominal US (Appendix 4.0)
Histology (8 subjects)	Baseline and last follow-up visit	Biopsies taken from treatment areas
Therapy Comfort	After every treatment	Therapy Comfort Questionnaire (Appendix 5)
Immediate response assessment	Immediately after each treatment	Complete in CRF
Subject satisfaction	Last follow-up visit	Subject Satisfaction Questionnaire (Appendix 5)
Safety- AE	During treatment and throughout study.	Examination of skin in the treated area, interview subjects, Adverse Events form, Occurrence and Severity Ratings, as well as relation to treatment, action taken and outcome

9. Adverse Events Reporting

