14.1 Analysis Sets

- Safety Analysis Set

The safety analysis set will include all subjects using Embrace procedures at least a single time.

- Performance Analysis Set

Performance analysis set will consist of all subjects providing at least one post treatment performance measurement.

- Treatment of Missing Values

Only observed data will be used; i.e. missing data will not be imputed.

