Appendix 1.0: Time and Events Schedule

Visit type Procedure	Visit 1*	Visit 2	Visit 3	Visit 4	Visit 5	Visit 6
	Screening Baseline Measures	Tx1 (same day or within 21 days after screening)	Tx2 (14 days after Tx1 +/- 2 days)	Tx3 (14 days after Tx2 +/- 2 days)	1 Month Follow-up (30 days after Tx3 +/- 7 days)	3 Month Follow- up (90 days after Tx3 +/- 10 days)
Medical History and Demographics	√					
Physical Exam	√					
Skin type	√					
Pregnancy Screening	√	√	√	√		√
Inclusion/Exclusion Criteria	√					
Informed Consent	√					
Photos	√				√	√
BMI/Height/Weight	√		√	√	√	√
Circumference	√		√	√	√	√
Caliper	√		√	√	√	√
Ultrasound	√					√
Histology-8 subjects (At selected sites)	√					√
Treatment		√	√	√		
Subject's Comfort		√	√	√		
Subject's Satisfaction						√
Skin response and AE		√	√	√	√	√
Concomitant Medication	√	√	√	√	√	√
Study End						√

* Screening and 1st treatment may occur on the same day and up to 3 weeks interval

	Safety and Efficacy of Trim II for Non-invasive Lipolysis and Circumference Reduction of Abdomen.	
	Protocol No: DO609924A SIRB ID: 8659	Rev. Date: Jun 3 2022

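### Section 6.1 restricts the primary efficacy analysis to subjects weight-stable over the study period but defines stability over the treatment period, and no other section settles which set is primary

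*Combined protocol and SAP*

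**What the plan says.** The primary efficacy endpoint (section 6.1) is the change in tape-measured abdominal circumference from baseline to the 3-month follow-up visit. Success is a statistically significant reduction. A starred note then restricts the analysis: "The primary effectiveness endpoint will be calculated based on those patients whose weight remains stable during the study period". The next sentence gives the only definition of stability: "A subject is defined as having maintained her weight during the treatment period if it remained within" ±3%, inclusive, "of baseline for the respective period".

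The synopsis row on study duration counts screening, three treatments and both follow-up visits. Appendix 1.0 sets Tx2 and Tx3 at 14-day steps (± 2 days) and the endpoint visit at "90 days after Tx3 +/- 10 days". Weight is recorded at both follow-up visits (sections 8.3 and 8.4, Appendix 1.0).

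Section 14.1 describes one efficacy set, with no weight criterion: "Performance analysis set will consist of all subjects providing at least one post treatment performance measurement". The readable text of 14.2 gives a paired t-test at two-sided 0.05 and names no set. The synopsis states the same endpoint and success criterion without the weight restriction.

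**The concern.** Two adjacent sentences in 6.1 give different windows for the rule that decides who enters the primary analysis. The sentence that sets the population covers the whole study. The sentence that says how to apply it covers only treatment, and its closing reference to a respective period is not explained.

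The trial has one arm and compares before with after, so a fall in mean weight is a rival explanation for a smaller waist. In the readable text the ±3% rule is the only stated protection against that explanation. If the check stops at the last treatment, most of that protection is lost: a subject can pass at Tx2 and Tx3, lose 5% of body weight by the endpoint visit, and still count as stable. If mean weight falls and the device does little, the two readings can give opposite verdicts on the primary criterion.

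**Working it through.** **1. Timeline (Appendix 1.0).** Tx3 falls 14 + 14 = 28 days after Tx1 (range 12 + 12 = 24 to 16 + 16 = 32). The endpoint visit is 90 days later (80 to 100), at day 28 + 90 = 118 (24 + 80 = 104 to 32 + 100 = 132). The share of the Tx1-to-endpoint interval after the last treatment is 90/118 = 76%. That the treatment period ends at Tx3 is inferred from this schedule; no section says so.

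**2. Which weights decide inclusion.** With same-day screening the baseline weight is taken on the day of Tx1. On the treatment-period reading, the Tx2 and Tx3 weights decide (days 14 and 28). On the study-period reading, the 1-month and 3-month weights decide as well (days 58 and 118).

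**3. Does another section settle it?** No. Section 14.1 has no weight criterion, 14.2 names no set in its readable text, and the synopsis omits the restriction. Section 6.1 is best read as a subset of the Performance Analysis Set, but no section says so.

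**4. Illustration of size.** The plan gives no effect size, SD or power for its 70 subjects, so there is no figure of its own to reproduce. Everything here is assumed except n = 70 and the test: mean weight 75 kg; 0.5 or 1.0 cm of circumference per kg; residual SD 2.5 cm; weight a random walk with SD 2% or 3% at the 3-month visit; same-day screening.

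Circumference change = slope × kg change + device effect + residual. Success is a significant reduction at two-sided 0.05, so nominal false success is 2.5%. Simulated results across the two slopes and two SDs:

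| Scenario | Treatment-period reading | Study-period reading | Opposite verdicts |
|---|---|---|---|
| No device effect, 1% mean loss | 18-56% false success | 4-19% | 14-38% of trials |
| No device effect, 0.5% mean loss | 7.5-18% | 3.5-8% | 5-12% |
| No device effect, no mean change | 2.3-2.5% | 2.3-2.5% | 2-3%, by chance |
| True 2 cm effect | – | – | at most about 0.5% |

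With screening 21 days before Tx1, the first row becomes 15-53% and 4-19%.

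Among subjects stable over the treatment period, the share outside ±3% at the endpoint visit is 13% (SD 2%) or 31% (SD 3%) with no mean change, and 18% or 33% with a 1% loss. Subjects kept of 70: 67-70 on the treatment-period reading. On the study-period reading 43-60 are kept with no mean change and 42-56 with a 1% loss, so about 42-60 overall.

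**5. Cost in power, and the all-subjects test.** SD of circumference change = √(2.5² + (slope × 75 × SD of weight change)²). A 1% mean loss is 0.75 kg, which shifts the mean by 0.375 cm (0.5 cm per kg) or 0.75 cm (1.0 cm per kg). The noncentrality for all 70 subjects is shift × √70 / SD, referred to a noncentral t with 69 df.

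| Weight SD | cm per kg | SD of change (cm) | Power for 1 cm, no mean change: all 70 / study-period set | All 70, no device effect, 1% loss: noncentrality, false success |
|---|---|---|---|---|
| 2% | 0.5 | √(2.5² + 0.75²) = 2.61 | 88% / 84% | 1.20, 22% |
| 2% | 1.0 | √(2.5² + 1.5²) = 2.92 | 80% / 79% | 2.15, 56% |
| 3% | 0.5 | √(2.5² + 1.125²) = 2.74 | 86% / 71% | 1.15, 20% |
| 3% | 1.0 | √(2.5² + 2.25²) = 3.36 | 69% / 64% | 1.87, 45% |

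The restriction costs 1 to 15 points of power. Without it, the all-subjects test has about 20-56% false success under a 1% loss, no better than the treatment-period reading.

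**The case against.** The harmful reading is the weaker one. The sentence that sets the population says study period, the synopsis counts both follow-up visits in the study's duration, and the respective-period phrase can be taken to match the window to the comparison, here baseline to 3 months. The rule, the ±3% threshold and the 3-month weighing are all prespecified. Omission from a synopsis is incompleteness, not contradiction. The large false-success figures also need several undocumented conditions at once: the less natural reading, little or no device effect, and a mean weight loss of 0.5-1%.

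All of this stands as a limit on size. It does not remove the conflict, because the only definition given names the other period and nothing elsewhere overrides it.

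A reader might infer more than the documents support: that the plan has no control for weight change, that the treatment period is defined to end at Tx3, or that the primary result will carry an 18-56% false-success rate. The documents do contain a weight rule, do not define the period, and give no weight drift, slope or SD. A reader might also fold in two nearby matters. One is that 7.2 calls subjects who do not complete treatment not evaluable while 14.1 admits anyone with one post-treatment measurement. The other is whether weight is taken at Tx1. Both are separate points and not part of this one.

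**Conclusion.** The wording conflict is real and should be corrected before analysis. Section 6.1 prescribes one window and defines another, and 14.1, the readable 14.2 and the synopsis leave the primary set unsettled. The likely cause is a drafting slip, and the study-period reading is the natural intent.

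The consequence is conditional. On the assumed inputs it is large only if mean weight falls and the device effect is small or absent. With no mean weight change there is no false-success inflation on either reading, and with a true 2 cm effect the choice almost never changes the verdict. Confidence is high for the textual conflict; the magnitudes are illustrative and move with the assumed slope, SD and drift.

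**What to change.** In 6.1, use one window that reaches the endpoint, for example: *A subject is weight-stable if every scheduled weight from baseline through the 3-month follow-up visit lies no more than 3% above or below baseline, limits included.* Using the 3-month weight alone performs almost the same and keeps slightly more subjects; either will do if it is stated. In 14.1, name the result as the primary efficacy set: members of the Performance Analysis Set who have baseline and 3-month circumference and are weight-stable as defined in 6.1. Repeat this in the synopsis.

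Optional and supportive only: the same t-test in all subjects with a 3-month measurement, to show the effect of selecting on post-baseline weight. It gives no protection against weight loss, so it must not be read as confirming the primary result.

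Cost: an amendment with the IRB approval that 10.3 requires, and no new data. Compared with analysing all 70, the primary set is smaller (about 42-60 on these assumptions) and power for a 1 cm effect falls by about 1-15 points. The corrected rule reduces weight-driven false success but does not remove it: 4-19% remains in the 1% loss illustration.
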